Abuse of opioids has resulted in a 57% and 717% increase in treatment admissions between 1992-2008 for heroin and prescription opioids, respectively (1). Opioid dependence is a chronic, relapsing disorder that is associated with greater health care services, more emergency room visits, prolonged disability, missed work days, and frequent overdose, resulting in an annual societal cost of more than \$8 billion (8 fold greater than nonabusers; (2, 3). Laboratory evaluations of opioids medications reveal robust and consistent between-person differences in self-report and physiological response to opioids (4-8), however no persistent demographic, drug use, and/or treatment characteristics have been identified that reliably predict susceptibility to develop opioid dependence (9-15). The phenomenon of varied individual response to drugs is not limited to opioid medications and clinically causes reductions in efficacy of medications and increased side effect profiles (16, 17). Pharmacogenetics, one approach to personalized medicine, addresses this phenomenon by using genotype information to predict phenotypic response (generally medication efficacy or safety; (18, 19). Regarding opioids, there is growing evidence to suggest a functional polymorphism in the OPRM1 gene that codes for the mu opioid receptor (MOR) may mediate individual response to opioid medications and have direct relevance for the development of opioid dependence (20-25). The most commonly researched single nucleotide polymorphism (SNP) of the MOR is a nucleotide exchange in exon 1 at the 118 position of the N-terminal domain (26), which results in an amino acid change from asparagine to aspartate at position 118 (Asn40Asp or A118G, rs1799971).

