**Study Days 2-5, Session Days:** The morning of each session, participants will be provided with a standardized breakfast, and cigarette smokers will be permitted 1 cigarette the morning prior to a session (1 additional cigarette will be permitted every 2 hours during the session). Sessions may take place either at the CRU or the BPRU, however all participants will reside overnight in the CRU. Participants will receive a standardized lunch and dinner. Beginning on Day 2, participants will receive a blinded study drug in the morning, will conduct a pain testing session approximately 60-90 minutes post-dose, and will provide self-report, observer-ratings, and physiological measures of drug effects for an additional 6-hours post-dosing. Each element is described in more detail below. Participants will also provide a blood sample (no more than 1 tablespoon) that will be analyzed for metabolic status. This sample can be collected at any point during Study Days 2-5.

**Pain Testing:** Participants will undergo 1 pain-testing session each day. Sessions will consist of pressure pain threshold, conditioned pain modulation, and temporal summation testing. Participants will be oriented to the study measures and pain testing apparatuses during the Admission Day. During the sessions, study drug will be administered under double-blind conditions in the morning. Salivary cortisol samples will be collected following completion of the pain testing session to evaluate the acute stress response to each pain stimulus, as a function of

drug (placebo vs. hydromorphone). Ratings of numeric rating scales will be used for data analysis, and participants will be asked to identify whether a placebo or active drug had been administered.

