**Pressure Pain Threshold:** The pressure pain threshold is defined as the kilopascals (kPA) value at which a mechanical stimulus is first judged to be painful. An electronic algometer with a 1cm^2 hard rubber probe will be applied two times to two different muscle groups in randomized order. Pressure will be applied at a constant rate of 30kPA/s until the participant first reports pain. A 30 second interval will be imposed between each stimulus presentation (105). The values in kPA will be averaged across administrations and muscle groups to create an index of pressure pain threshold. Administering the stimulus at multiple anatomic locations increases the reliability of the pressure pain threshold. Possible effects of laterality and muscle group will be evaluated to determine if threshold outcome measures should be separated into subgroups.

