We have chosen to deliver doses lower than those administered by that study so we may evaluate whether there are individual differences in the ability to detect the low dose of hydromorphone. Participants in our study will receive three active hydromorphone doses. The first dose participants will receive is the mid-level dose, which will be administered on study Day 2. Any participant who has a negative reaction to this dose will be discharged from the study. The participants will receive placebo, low, and high doses on Days 3-5 of the study; the order of doses will be randomized and counter-balanced. These doses were deemed safe in the same participant population in the Walsh study, they produced a documented detectable range of subjective effects, and they represent suprathreshold doses consistent with those abused recreationally. Ultimately, we feel confident these dose values do not impose any unique risk above and beyond that presented by the administration of hydromorphone.

Generic powdered hydromorphone will be encapsulated using size 0, opaque, hard gelatin capsules; placebo will be size and weight matched and will contain microcrystalline cellulose filler. A pharmacy member with no participant interaction will conduct the dose randomization. All medication administration will be supervised and a medical staff member will be available to address any adverse events or to break the medication blind.

- b. Justification and safety information if FDA approved drugs will be administered for non-FDA approved indications or if doses or routes of administration or participant populations are changed.

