**Association Model:** Our primary goal is to demonstrate the impact of SNP variation across OPRM1 on variability in response to hydromorphone across time and dose. Association analyses will be performed by modeling genotype at each SNP in a general linear model. In its simplest form this test, commonly termed the measured genotype analysis (137), models the influence of genotypic variation at a given locus on variation in the quantitative trait, essentially a one-way Analysis of Variance (ANOVA). This approach provides a distinct advantage in that it can easily be extended to a two-way ANOVA to model genotype effects across 3 different doses of drug. In addition, the flexibility of the GLM allows incorporation of ancestry covariates and environmental moderators or mediators. We will examine the impact of OPRM1 at each time-point in separate analyses and account for the multiple testing using LD-adjusted Bonferroni correction (see below).

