**Analysis of pain testing sessions:** We hypothesize that OPRM1 SNP variants will exhibit greater pressure pain thresholds, greater CPM efficiency, lower hydromorphone-related analgesia, and lower cortisol stress response than participants with the major allele, and that results will be positively correlated with response to self-report and physiologically-mediated hydromorphone drug effects collected during days 3-5. Pressure pain threshold will be estimated by averaging the results of the 2 administrations to radiobrachialis and quadriceps muscle groups. We will generate a CPM index for each participant [(mean pressure pain threshold during cold pressor)/(mean pressure pain threshold prior to cold pressor)] x 100 (90). These values will provide a quantitative measure of percent change in the test stimulus (i.e., pressure point threshold). Mixed effects regression models with a random intercept will be used to compare dependent variables (pressure pain threshold, DNIC threshold, DNIC index) as a function of within-subject drug effects (placebo vs. hydromorphone), and between-subject effects of OPRM1 SNP analysis will be conducted as specified in Aim 1. Gender, age, and race have been associated with response to pain and the CPM test (146-148). Gender will be evaluated using independent subgroup analyses and age and race will be included as covariates. Finally, subscale scores of self-report measures of pain and coping strategies will be compared between the two genotype groups using independent samples t-tests, and drug identification data will be compared using a chi-square for each drug condition. We expect that both experimental manipulations will induce pain in the minor and major allele groups, and that participants with the minor allele will demonstrate lower sensitivity to pain (e.g., greater pressure pain magnitudes), lower NRS ratings of pain, lower cortisol response to painful stimuli, and lower analgesic relief from hydromorphone compared to the major allele participants.

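### The pain model has a random intercept only and a two-level drug factor, so its standard error for analgesia is not reliable when three active sessions are set against one placebo session

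*Combined protocol and SAP*

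**What the plan says.** All analysis text is in Section 7c of the combined protocol and SAP.

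- **Pain model** (Analysis of pain testing sessions): "Mixed effects regression models with a random intercept will be used to compare dependent variables", namely pressure pain threshold, DNIC threshold and DNIC index, "as a function of within-subject drug effects (placebo vs. hydromorphone". No random drug slope or other covariance structure is named, and nothing says how the three active doses enter.
- **Genotype in the pain analysis** (same paragraph): "between-subject effects of OPRM1 SNP analysis will be conducted as specified in Aim 1". The Aim 1 model (Association Model) is a general linear model per SNP, of which the plan says "it can easily be extended to a two-way ANOVA to model genotype effects across 3 different doses of drug". No genotype-by-drug term is written for the pain outcomes.
- **Sessions:** Section 4a says "Participants will undergo 1 pain-testing session each day", on Days 2 to 5. Section 6a puts the mid-level dose on Day 2 and then says "The participants will receive placebo, low, and high doses on Days 3-5 of the study". That makes three active sessions and one placebo session per person.
- **Values per session:** Section 4a says "The values in kPA will be averaged across administrations and muscle groups to create an index of pressure pain threshold". The conditioned pain modulation index is likewise averaged over its two trials, so each outcome has one value per session.
- **Hypothesis:** lower hydromorphone analgesia in minor-allele carriers is hypothesised in Sections 2 and 7, and Section 7a lists analgesic efficacy among the primary outcome variables.

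**The concern.** A random intercept removes stable differences between people in pain level. It does not represent differences between people in response to the drug. Three active sessions from one person share that person's sensitivity, yet under a two-level factor they enter as if each were a fresh replicate of the drug effect. The trial is built on varied response. Section 3 states "Laboratory evaluations of opioids medications reveal robust and consistent between-person differences in self-report and physiological response to opioids".

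Analgesia is by definition an active-minus-placebo quantity, so a genotype effect on analgesia is a genotype-by-drug contrast. If its error term does not match the design, the p-values and confidence intervals for a primary outcome variable are wrong by an amount nobody can state in advance.

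**Working it through.** The plan gives no standard error, variance or power for the pain model, so there is no figure of its own to reproduce. The check compares the variance that the model would report with the true variance, for complete data.

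**Inputs from the documents:** N = 100 completers; one placebo and three active sessions each; one value per session; doses of 2, 4 and 8 mg.

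**Assumptions (not in the documents):** residual SD e = 1; a person's response at dose d is w_d × (m + u), where m is the mean effect and u has SD s. The weights w_d give the dose profile, with the top dose set to 1. Tests are two-sided. Let W be the mean of the three weights and SS the sum of their squared deviations from W.

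**Step 1. One placebo and one active value per person.** Model variance of a person's contrast = 2e² + s². True variance = 2e² + s². The ratio is 1, so the model reduces to a paired comparison and is correct.

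**Step 2. Three active rows against one placebo row, two-level factor.**

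- True variance of (mean active − placebo): 4/3 e² + s²W².
- The residual pools three within-person degrees of freedom, one carrying the contrast and two carrying differences among active sessions. Its expectation is e² + s²W²/4 + (m² + s²)SS/3.
- Model variance = 4/3 of that residual: 4/3 e² + s²W²/3 + (4/9)(m² + s²)SS.
- Model minus true = (4/9)(m² + s²)SS − (2/3)s²W².

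The first term comes from dose differences left in the residual and makes the standard error too large. The second comes from the missing slope and makes it too small. The sign depends on the dose profile. The same ratios apply to a genotype-by-drug contrast, because both variances are multiplied by the same group-size factor.

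**Step 3. Numbers.** The SE ratio is the square root of model over true variance. Actual error at nominal .05 is 2 × [1 − Φ(1.96 × ratio)].

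| Dose profile | s, m | Model var. | True var. | SE ratio | Error at .05 |
|---|---|---|---|---|---|
| Equal (1, 1, 1): W = 1, SS = 0 | 0.5, any | 1.417 | 1.583 | 0.946 | .064 |
| | 1, any | 1.667 | 2.333 | 0.845 | .098 |
| | 2, any | 2.667 | 5.333 | 0.707 | .166 |
| Proportional to dose (.25, .5, 1): W = .583, SS = .292 | 1, 0.5 | 1.609 | 1.674 | 0.980 | .055 |
| | 1, 1 | 1.706 | 1.674 | 1.010 | .048 |
| | 2, 1 | 2.435 | 2.694 | 0.951 | .062 |
| | 2, 2 | 2.824 | 2.694 | 1.024 | .045 |
| Top dose only (0, 0, 1): W = .333, SS = .667 | 1, 0.5 | 1.741 | 1.444 | 1.098 | .031 |
| | 1, 1 | 1.963 | 1.444 | 1.166 | .022 |
| | 2, 1 | 2.963 | 1.778 | 1.291 | .011 |
| | 2, 2 | 3.852 | 1.778 | 1.472 | .004 |

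Simulation of the genotype-by-drug test (20,000 trials per row, assumed 30/70 genotype split) agrees: .063, .098 and .164 for the equal profile, .044 to .065 for the proportional one, and .004 to .032 for top dose only.

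**Step 4. Dose as a four-level factor, still with a random intercept only.** For one dose against placebo, with an equal person-specific effect across doses, model variance is 2e² + s²/2 and true variance is 2e² + s². For s = 0.5, 1 and 2 the SE ratios are √(2.125/2.25) = 0.972, √(2.5/3) = 0.913 and √(4/6) = 0.816. Coding dose as a factor reduces the shortfall in this case but does not remove it.

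**Step 5. One contrast per participant.** Analysing each person's mean active minus placebo value gave .048 to .053 at nominal .05 in all eleven settings of the table.

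**The case against.** The strongest reply is that the plan never says the three active sessions enter as separate rows. If they are averaged, or one dose is compared with placebo, Step 1 applies and nothing is wrong. That stands, and it is why the point is conditional.

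A reader might infer that standard errors are always too small. The documents do not support that. It needs a person's response to be much the same at all three doses, in a trial that Section 4a describes as a dose-response evaluation. Section 6a reports the two lowest pilot doses of a cited study as inactive, yet calls the chosen doses suprathreshold, so the dose profile is open.

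A reader might also infer that the SNP tests at .001 are inflated several-fold. In the equal-response case the error at nominal .001 would be about .002 to .020. But the .001 level belongs to the SNP tests, which the plan sends to the Aim 1 linear model. If Aim 1 is run on one change score per person, a missing slope is irrelevant. If it is run on dose-level rows without a subject term, that is a different fault.

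Nor does a random intercept assume that everyone responds equally: individual differences go into the residual, and harm arises when several sessions share them. It is also fair that the drug main effect is not itself a study hypothesis, and that the statement in Section 3 concerns self-report and physiological response rather than pain thresholds.

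These replies limit the claim. They do not show that the written error term is right for the data the trial will collect.

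**Conclusion.** The point holds in conditional form. With three active rows and one placebo row per person, the specified model gives a reliable standard error for the drug effect, or for a genotype-by-drug contrast tested in it, only when two opposing terms happen to cancel. Over the assumed values, actual error at nominal .05 ranges from .166 (equal response across doses, s/e = 2) to .004 (top dose only, s/e = 2 and mean effect 2e). It is .045 to .062 when response is proportional to dose.

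These figures illustrate the dependence and do not predict the trial's error rate. They rest on assumed s/e, mean effects and dose profiles, on complete data and on the pooled reading of the drug factor. The documents supply no variances that would settle size or direction. What is certain is that the plan leaves the dose coding and the genotype-by-drug test unwritten for a primary outcome variable, and that a method valid under all these profiles is available from the same data.

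**What to change.** State in Section 7c how the three doses enter the pain analysis, and write out the genotype test of analgesia. Either of two forms will do:

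1. Compute one active-minus-placebo contrast per participant for each pain outcome: the mean of the active doses, or a prespecified single dose or dose-slope contrast. Analyse it in the per-SNP general linear model with the planned ancestry, age and race covariates.
2. Fit a mixed model with dose as a factor, a genotype-by-dose term, and either an unstructured covariance or a participant-level random slope for drug or dose in addition to the intercept.

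The first form is simpler and joins directly to the Aim 1 analysis. The contrast should be named before the data are seen.

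The cost is SAP wording and fewer error degrees of freedom: before covariates, 100 − 2 = 98 for the contrast, against 3 × 100 − 2 = 298 for the pooled model. No new data are needed. Confidence intervals may widen or narrow to their correct width. In the table the standard error would rise by up to 41% (1/0.707) or fall by up to 32% (1 − 1/1.472).

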
#### 2. Objectives (include all primary and secondary objectives).

The primary aim of this study is to examine the associations of specific polymorphisms in the OPRM1 gene with mu opioid receptor (MOR)-mediated effects. We hypothesize the minor A118G SNP allele and OPRM1 tagging SNPs will predict more reinforcing properties of hydromorphone, (e.g., higher self-report ratings of high and drug-liking) and greater opioid-induced physiological changes (e.g., pupil diameter, blood pressure), decreases in cortisol levels as a function of the degree of pleasant effects of hydromorphone, and steeper discounting curves on a delay-discounting task. The secondary aim of this study is to examine the associations of specific polymorphisms in the OPRM1 gene with laboratory measures of pain. We hypothesize the minor A118G SNP allele and OPRM1 tagging

SNPs will predict higher pain threshold on two experimentally-induced laboratory measures of pain, lower analgesic efficacy in response to experimentally-induced pain, and lower cortisol response to painful stimuli. Finally, as an exploratory aim, we will examine the contribution of sex to the primary and secondary aims.

**3. Background** (briefly describe pre-clinical and clinical data, current experience with procedures, drug or device, and any other relevant information to justify the research)

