Additional, well-controlled studies are needed to understand and advance our knowledge regarding the effect of the A118G SNP and additional OPRM1 tagging SNP variants on baseline pain tolerance, and pain tolerance under conditions of opioid analgesic treatment. Only two studies have examined the contribution of the A118G on pain tolerance in controlled laboratory settings (78, 81). The first study reported positive associations between A118G and pain on two of the three pain tolerance tests conducted, but did not evaluate tolerance to pain following opioid agonist administration (78, 81). The second study reported a positive association with OPRM1 on one test of pain following oxycodone administration, but did not evaluate additional pain tolerance tests, which is important given the high rate of individual variability among pain testing methods (78, 81). Neither study sampled across the OPRM1 gene and or was designed to prospectively evaluate gender, which is critical because of the robust gender-specific effect that exists on pain and its potential interaction with the OPRM1 gene (41). The current study will extend upon these studies by evaluating the effect of the A118G SNP and OPRM1 gene using a quantitative sensory testing (QST) paradigm, under conditions of double-blind and placebo-controlled hydromorphone administration, and will conduct gender specific analyses. Women will only be enrolled during the first two weeks of their cycle (confirmed via progesterone analysis) to minimize hormonal effects on pain, which will be the most rigorous evaluation of OPRM1 and pain within gender to date. Further, one of our pain tests will activate the diffuse noxious inhibitory control (DNIC) system, which is mediated by the endogenous opioid system, hypothesized to be a model of chronic pain, and believed to contribute to opioid-induced hyperalgesia (97). No prior study has used the DNIC procedure to evaluate OPRM1 effects on pain tolerance, which is critical because of the established functional relationship between the OPRM1 and the endogenous opioid response (26, 98). The results will advance our understanding of the OPRM1 contribution to pain tolerance and response to medication, help elucidate the

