#### 4. Study Procedures

- a. Study design, including the sequence and timing of study procedures (distinguish research procedures from those that are part of routine care).

**Study Overview:** This study will be a between-group (total completer N=100) evaluation of genotype and sex, and a within-subject evaluation of opioid dose-response. The study will be conducted over 5 days (4 nights) at the Behavioral Pharmacology Research Unit (BPRU) and a residential clinical research unit (CRU) (Figure 1). Day 1 will be an Admission day. Days 2-5 will consist of blinded study drug administration in the morning, 1 pain testing session, and self-report/physiological measures of drug effects for 6 hours post dosing. Participants will receive double-blind doses of oral hydromorphone (2mg, 4mg, 8mg) (99-102) or weight and color-matched placebo in a randomized, counter-balanced research design.

**Screening Visit:** Participants will complete a brief phone screen to determine initial eligibility and will be invited to complete an in-clinic screen. Participants will sign an informed consent form with a study staff member to begin the Screening visit. To reduce expectancy effects, the consent will inform participants the study drug may consist of one or more of numerous different drug classes (e.g., opioids, stimulants, over-the-counter medications), a common practice in laboratory based studies of drug effects (103, 104). Following consent, a staff member will administer a battery of measures to establish study eligibility (see Study Measures below). A urine sample will be collected and tested for evidence of illicit drugs and to establish medical eligibility. A blood sample of no more than 2 tablespoons will also be collected from eligible participants for medical and genotype analysis. Participants will also be asked to provide a second blood sample (2 additional tablespoons) that will be collected at either Screening or Admission and stored for future genetic analysis. This will be voluntary. Participants who meet eligibility criteria (including results of laboratory blood tests) will be scheduled for an Admission day.

**Study Day 1, Admission Visit:** Participants will complete a brief history and physical to determine final study eligibility and will be admitted to the CRU for 5 days (Admission day + 4 session days). During the Admission day, participants will be familiarized with the pain testing procedures and the measures used during session days 2-5.

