## 7. Study Statistics

a. Primary outcome variables. The primary outcome variables are self-reported ratings of drug high and liking, changes in pupil diameter and blood pressure, pain threshold on 2 laboratory measures of pain, and analgesic efficacy in response to laboratory-induced pain. We expect that individuals with the minor allele of the A118G SNP and other

tagging SNPs across the OPRM1 gene will find hydromorphone more reinforcing (e.g., higher self-report ratings of high and drug-liking) and exhibit greater opioid-induced physiological changes (e.g., pupil diameter, blood pressure). Research also suggests the OPRM1 gene may also confer greater sensitivity to the negative effects of opioids, which may be observed as measuring greater ratings of nausea. We also hypothesize the minor allele and other tagging SNPs across the OPRM1 gene will produce higher pain threshold on 2 laboratory measures of pain, and lower analgesic efficacy in response to laboratory induced pain.

**b. Secondary outcome variables.** Decreases in cortisol levels as a function of the degree of pleasant effects of hydromorphone and painful stimuli, delay-discounting curves, and the effect of sex on all outcome measures. We hypothesize that individuals with the minor alleles will have greater decreases in cortisol levels as a function of the degree of pleasant effects of hydromorphone, lower cortisol in response to painful stimuli, and steeper discounting curves on a delay-discounting task. Finally, although we expect that the A118G will be associated with these effects, we hypothesize that several of the additional OPRM1 tagging SNPs will contribute to effect magnitude.

**c. Statistical plan including sample size justification and interim data analysis:** The aims of the proposed study will explore the impact of genetic variation across the OPRM1 gene on hydromorphone response. There are specific steps we describe below to assure that we interrogate all known functional variation across the OPRM1 gene, adequately cover all other variation using appropriately selected tagging SNPs, prevent spurious associations due to population stratification by accounting for local ancestry, and properly control the Type I error rate.

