**9. Benefits**

Description of the probable benefits for the participant and for society: The long-term goal of this research is to investigate individual differences in response to opioids, and identify genetic differences that contribute to variations in the susceptibility of opioid dependence. The objective of this application is to determine whether the OPRM1 gene predict one of several opioid-mediated effects using a rigorous, controlled laboratory study among healthy individuals with no history of drug dependence and whether this effect differs as a function of gender. This study will constitute the most controlled, rigorous, comprehensive examination of the OPRM1 gene association with opioid-mediated effects to date. We expect that genotype will be associated with several opioid-mediated effects. These results are expected to have a positive impact by advancing our understanding of the association between the OPRM1 gene and opioid-mediated effects, including susceptibility for opioid dependence. These data will provide positive contributions to the field of pharmacogenomic medication prescribing, the development of opioid dependence prevention strategies and interventions to treat comorbid pain and opioid dependence, and will have implications for other MOR-mediated effects, including alcohol dependence.

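### The protocol asks whether the OPRM1 effect differs by sex, but the only analyses it states are separate within-sex ones, which neither estimate nor test that difference

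*Combined protocol and SAP*

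**What the plan says.** Sex appears as a study question in several places:

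- Section 2 (Objectives): "as an exploratory aim, we will examine the contribution of sex to the primary and secondary aims".
- Section 3 (Background) faults earlier laboratory pain studies for not being designed to evaluate gender, citing the "robust gender-specific effect that exists on pain and its potential interaction with the OPRM1 gene".
- Section 4a (Study Overview) describes a between-group "evaluation of genotype and sex".
- Section 7b lists "the effect of sex on all outcome measures" under secondary outcome variables.
- Section 9 (Benefits) includes in the objective "whether this effect differs as a function of gender".

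The methods stated for it are few:

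- Section 3 says the study "will conduct gender specific analyses".
- Section 7c, analysis of pain testing sessions: "Gender will be evaluated using independent subgroup analyses and age and race will be included as covariates".
- Section 7c, power paragraph: more than 80% power at alpha .001 for an effect of .67 in sex subsamples of 50.
- Section 7c, association model: "the flexibility of the GLM allows incorporation of ancestry covariates and environmental moderators or mediators". Sex is not named there.

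Section 7d sends a mid-enrolment report by masked sex group to an independent panel. That report is not broken down by genotype.

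**The concern.** Whether a genotype effect differs between men and women is a question about a difference between two effects. Fitting one model in men and another in women gives each effect on its own. It gives no estimate of the difference, no standard error for it and no test. Nor does it give a sex main effect, so it also fails the other natural reading of the Section 7b item. The pain paragraph puts age and race into the model but takes gender out of it. For the drug-effect outcomes, the only sign of the intended method is the subsample power sentence.

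Without a stated comparison, the easy way to read two sets of results is to note which sex is significant. A genotype effect that is the same in both sexes could then be reported as specific to one. What is at stake is any statement about sex. The full-sample genotype conclusions do not rest on this analysis.

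**Working it through.** **Inputs from the documents (Section 7c, power paragraph).** N = 100 completers, 50 per sex; alpha .001; effect size defined as Cohen's d between genotype groups; claimed power above 80% at d = .67 within a sex; an effect of 1.2 cited from earlier work.

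**Assumptions.** Two genotype groups, two-sided tests and one measure per person. The documents give no carrier share, so every genotype split is assumed: 25/25, 15/35 or 10/40 within each sex.

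**Step 1: the plan's own figure.** Power within one sex from the noncentral t with 48 df, d = .67, 25/25, alpha .001, is 14.6%, not above 80%. The stated power does not reproduce under the stated definition. That is a separate matter, but it is why both versions appear below.

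**Step 2: chance that exactly one sex is significant when the true effect is the same in both.** The two samples are independent, so with power p in each the chance is 2p(1 − p).

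At the plan's claimed power: 2 × .80 × .20 = 32%.

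Recomputed:

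| Alpha | Split per sex | d | p | 2p(1 − p) |
|---|---|---|---|---|
| .001 | 25/25 | 0 | .001 | 0.2% |
| .001 | 25/25 | .30 | .011 | 2% |
| .001 | 25/25 | .45 | .037 | 7% |
| .001 | 25/25 | .67 | .146 | 25% |
| .001 | 25/25 | 1.2 | .762 | 36% |
| .001 | 15/35 | .67 | .108 | 19% |
| .001 | 10/40 | .67 | .067 | 12% |
| .05 | 25/25 | 0 | .050 | 9.5% |
| .05 | 25/25 | .67 | .641 | 46% |

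The .05 rows apply only if the planned multiplicity correction were not used for the sex analyses.

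**Step 3: the direct test in the same setting.** In 200,000 simulated trials with d = .67 in both sexes, 25/25 and alpha .001, exactly one sex was significant in 25.0%. The genotype-by-sex test was significant in 0.09%, which is its nominal rate.

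**Step 4: precision of the direct estimate.** In SD units the interaction SE is the square root of the sum of 1/n over the four genotype-by-sex cells. The 95% half-width is t(.975, 96 df) = 1.985 times the SE. The difference detectable with 80% power, by normal approximation, is (z + .842) × SE, with multiplier 2.802 at alpha .05 and 4.132 at alpha .001.

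| Split per sex | SE | 95% half-width | Detectable, .05 | Detectable, .001 |
|---|---|---|---|---|
| 25/25 | √(4/25) = 0.40 | 0.79 | 1.12 | 1.65 |
| 10/40 | √(2/10 + 2/40) = 0.50 | 0.99 | 1.40 | 2.07 |

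**The case against.** The strongest reply is that sex is exploratory in Section 2, where the wording asks only about its contribution, and that Section 3 speaks of evaluating OPRM1 and pain within gender, which within-sex models do. Separate models also yield two estimates and standard errors, so the between-sex contrast is one subtraction away. Stratifying has some rationale: women are enrolled only in part of the cycle, and Section 5 allows birth control as a covariate. The error rates above describe a misreading that the plan never says it will make. They assume one measure per person, whereas the pain analysis is a repeated-measures mixed model. Finally, the interaction test is weak.

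Some of this stands. The harm depends on an unstated reading rule. The rates are illustrative and run from 0.2% to over 30% on inputs the documents do not give. The 32% figure rests on a power claim that does not reproduce.

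The rest does not remove the gap. Section 9 states effect modification as part of the objective, and an exploratory question still needs an estimate that addresses it. The subtraction is possible, but nothing says it will be done. A covariate that exists only in women can be handled in a pooled model. Low power for the interaction is a fact of the sample size whichever analysis is used: separate p-values hide it, and a confidence interval shows it.

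**Conclusion.** The concern holds. No section specifies a genotype-by-sex term, a contrast of the within-sex estimates, or a rule for comparing them, so the stated analysis does not answer the sex question. This follows from the text alone and does not depend on the power figures.

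The consequence is confined to conclusions about sex. If those were drawn from which sex is significant, the false pattern would be rare with no genotype effect and would become common as the shared effect approaches the sizes the plan has in mind. The exact rate cannot be fixed without the carrier share and the within-person correlation. The plan should be changed, because the change is cheap, but the point does not threaten the main genotype analysis.

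**What to change.** In Section 7c:

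- Fit the full N=100 model with sex and genotype-by-sex terms, adding genotype-by-sex-by-dose where analgesia is the outcome.
- Base every statement about a sex difference on the interaction estimate and its confidence interval.
- Report within-sex estimates from the same model, labelled descriptive.
- State the same rule for the drug-effect outcomes, and say how a women-only birth control covariate enters the model.
- Say whether the sex question is exploratory (Section 2) or secondary (Section 7b).

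A sex main effect would also remove sex variance from the between-person genotype comparison of pain threshold, though not from within-person drug contrasts. The documents do not allow that gain to be sized.

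The cost is plan wording only: no new data, participants or procedures. The plan should admit the drawback that only very large sex differences are detectable (1.12 SD at alpha .05 in the best case worked above). The change makes the answer about sex honest more than it makes it precise.
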